Protocol: Evaluation of oral condition and the effect of dental treatment on physical parameters of athletes

Researcher: [name]

Approval of the Research Ethics Committee in Brazil: 93416718.1.0000.0081

Approval date: 09/August/2018

Main goal

Evaluate the oral condition and propose dental treatment according to the needs of athletes linked to the Faculty of Physical Education of the Santo Amaro University.

Secondary objectives.

- Comparing the athlete's performance through physical tests of strength, speed, endurance, before and after dental treatment;
- Relate the oral conditions found with the specific habits of each sport;
- Assess the effect of biofilm control on the oral and performance conditions of the evaluated athletes.

Protocol:

This research project will comply with Resolution No. 196, of October 16, 1996, of the National Health Council, and the Dental Professional Code of Ethics (Resolution CFO No. 042/2003).

All recruited individuals will be offered verbal and written explanations of the objectives, methodology, benefits and possible risks related to participation in the project. Thus, individuals who accept to participate in the study, will sign the Free and Informed Consent Term, previously evaluated and approved by the Research Ethics Committee involving human beings of UNISA.

3.1-Experimental design

Students and / or athletes linked to the Faculty of Physical Education of the University Santo Amaro must be evaluated. According to an initial survey, about 120 individuals should be examined. Clinical parameters such as decayed, lost and / or filled dental index (CPO) and periodontal parameters such as probing depth (PS), clinical level of insertion (NCI), plaque index (IP) and bleeding index (IS) will be evaluated . Physical tests of strength, speed and resistance should be performed and periodontal therapy should be performed according to the needs presented by each individual. After 90 days, new clinical examinations and physical tests should be performed.

3.2-Selection of patients

Individuals practicing physical activities linked to UNISA will be included. Initially, we will have a convenience sample that will later be stratified into groups for evaluation and analysis. Individuals with systemic pathologies, smokers, should be included in the study

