Patients with any of these characteristics should be excluded from the study: pregnancy or lactation, use of antibiotics in the last 3 months, phenytoin, calcium antagonists, cyclosporine or anti-inflammatory drugs one month before the initial consultation, use of oral or replacement contraceptives hormonal, periodontal treatment in the 6 months prior to the start of the study.

After being properly informed about the nature of the study, individuals must sign a free and informed consent form.

Patients will be submitted to periodontal treatment in undergraduate and graduate clinics at the UNISA Department of Dentistry, according to the needs presented.

3.3-Clinical evaluation

Patients will be evaluated by a previously trained and calibrated periodontist. Of the sample, 10% will be examined twice for each of the clinical criteria evaluated, in order to obtain the inter-examiner diagnostic reliability measured by Kappa statistics (between 0.8 and 1.0) and intra-examiner using the standard error of the measurement. (EPM). In the periodontal clinical examination, measurements will be obtained for probing depth and clinical level of insertion performed at six points per tooth: mesio buccal, labial mesio, buccal mesio, mesio lingual / palatine, lingual / palatine medium, this lingual / palatine, using periodontal probe manual (PCPUNC 15, Hu-Friedy, Chicago, USA). For Plaque Index and Gingival Index (Ainamo & Bay, 1975), dichotomous evaluation will be performed on the faces: vestibular, mesial, distal and lingual / palatal.

Patients will be observed in two stages, as shown in figure 1, prior to the start of treatment (T0) where clinical examinations will be performed, radiographs will receive dental scaling and root planing treatment (T1) and 90 days after therapy (T2) will be evaluated again (Nakamura-Minami, et al., 2003; Figueredo et al., 2004; Gomi, et al., 2007).

3.4- Physical Evaluation

The following demographic variables will be assessed: age, sex, race and education. We will adopt the following inclusion criteria: Be a practitioner of one of the modalities investigated for more than 5 years and perform more physical activity than the minimum recommendations per week, for this analysis we will use the international physical activity questionnaire.

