The evaluations performed will be: Aerobic running performance evaluation test, critical speed in swimming, body composition evaluation, muscle strength through the 1RM test in the bench press and short-term heart rate variability at rest. The evaluations proposed by the present study will be carried out in three days, with an interval of 24 hours.

Risk stratification for cardiovascular events during exercise will be performed according to the ACS recommendations. An anamnesis will be performed based on the following cardiovascular risk factors: age, family history of cardiovascular disease, smoking, high blood pressure, dyslipidemia or hypercholesterolemia, diabetes or hyperglycemia.

3.5- Periodontal Therapy

Periodontal treatment will start after physical tests of strength, speed and endurance. The individuals evaluated in this study will receive instructions on oral hygiene, including brushing technique and use of dental floss / tape, and treatment of dental scaling and root planing (RDAR).

After anamnesis, the individuals included will receive instructions for individualized oral hygiene. The treatment of RDAR will be performed in a single session (full-mouth disinfection) according to the established protocol (Quirynen et al 1999, 2006), with two sessions carried out in 24 hours.

The individuals will be treated by a single periodontist and the scraping and planing procedures will be performed on all teeth as follows: local anesthetic infiltrative type of the areas to be treated, RDAR using Gracey 5/6 carbon steel curettes, 11/12, 13/14 and MacCall 13/14, 17/18 curettes, according to their therapeutic indications. Polishing the quadrants treated with abrasive paste; oral hygiene instructions including brushing of the Bass type, dental floss and sometimes toothbrush inter dental or unitufo (Apatzidou; Riggio, Kinane, 2004, Jervoe-Stormet al., 2006).

After the dental scaling and root planing procedures, 90 days should be waited for reassessment and conducting the new clinical and physical exams. The individuals will then be referred to the clinics in operation at the Faculty of Dentistry of UNISA according to their needs.

3.6 - Statistical analysis

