Analysis of variance (ANOVA) will be used to compare the averages of dental clinical values and physical tests. Parametric and non-parametric values should be analyzed. The analyzes and graphs of the present study will be performed with the aid of the statistical program graphPad Prism version 4.0. The data present in the graphs will be expressed as mean \pm SEM (standard error of the mean).

With the objective of studying the association between the probing depth, presence of plaque, presence of bleeding and existence of maintenance variables, as the physical exercises performed before and after dental treatment generalized estimating equation models should be used. The score test will be used to test the target hypotheses, because the observations are dependent. The Gaussian with an identity link function will be applied. The half-normal probability plot with a simulated envelope¹⁵ made it possible to observe that the model was well adjusted. R software, version 3.2.5, will be used to analyze the data and a significance level of 5% was considered for all the tests.

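### Does testing strength, speed and endurance each at 5%, with no main performance outcome or adjustment, call for a multiplicity rule in section 3.6?

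*Combined protocol and SAP*

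**What the plan says.** The main goal is to "Evaluate the oral condition and propose dental treatment according to the needs of athletes". Performance enters as the first secondary objective: "Comparing the athlete's performance through physical tests of strength, speed, endurance, before and after dental treatment". The three domains are listed without a ranking.

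Section 3.4 lists the evaluations: "Aerobic running performance evaluation test, critical speed in swimming, body composition evaluation, muscle strength through the 1RM test in the bench press", together with resting heart rate variability, so there are five in all. Bench press 1RM is described as a strength test and the swimming test as a speed test. No evaluation carries the word endurance; assigning aerobic running to that domain is an inference, though a natural one.

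Under section 3.5, "90 days should be waited for reassessment and conducting the new clinical and physical exams". In section 3.6, "Analysis of variance (ANOVA) will be used to compare the averages of dental clinical values and physical tests". The same section plans generalized estimating equation (GEE) models with score tests that also involve the physical measures, and sets the level once: "a significance level of 5% was considered for all the tests". It names no family-wise error rate, main performance outcome, testing order or adjustment. It also contains no rule by which one significant test would establish that performance in general had changed.

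**The concern.** A 5% level limits the error of one test. It does not limit the error of a conclusion that may rest on whichever of several tests turns out significant. The trial's title refers to an effect on physical parameters, so a general statement about performance is a likely headline. With no test named in advance, the one to emphasise could be picked after the 90-day results are known. A reader who took such a statement as carrying a 5% error rate would be misled by a factor of up to nearly three.

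**Working it through.** **Inputs.** The level is 0.05 per test (section 3.6). The three domains come from the secondary objective. The only sample size is a survey count, "about 120 individuals should be examined" (section 3.1). The plan gives no correlation between tests, no sidedness and no error rate for a family of tests, so it has no figure of its own to reproduce. Two-sided testing, one test per domain and a common correlation r are assumptions made here.

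**Error rate under an any-one-of-three claim, with nothing truly changing.** For independent tests it is 1 − (1 − 0.05)³ = 1 − 0.857375 = 0.1426. For correlated tests, the probability that at least one of three equicorrelated normal statistics exceeds 1.960 in absolute value was found by numerical integration:

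| r | At least one false change, each test at 5% |
|---|---|
| 0 | 14.3% |
| 0.3 | 13.6% |
| 0.5 | 12.5% |
| 0.7 | 10.9% |
| 0.8 | 9.8% |
| 0.9 | 8.4% |
| 1 | 5.0% |

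Whatever the correlation, the rate cannot exceed 3 × 0.05 = 15%. Counting all five evaluations in section 3.4 gives 1 − 0.95⁵ = 22.6% at r = 0 and 18.3% at r = 0.5. The size therefore depends on an unknown correlation and on how many evaluations are taken to measure performance.

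**Error rate if each domain is reported as its own result.** It is 5% for each statement, as section 3.6 says. No calculation in the plan is wrong on this reading.

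**What Holm would gain.** When nothing changes, Holm rejects at least once only if the smallest p-value is at or below 0.05/3 = 0.0167. That happens with probability 1 − (1 − 0.0167)³ = 4.9% at r = 0, and 4.8% and 4.5% at r = 0.3 and 0.5.

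**What Holm would cost.** Take one paired comparison per test, which is an assumption because the plan names only ANOVA. The detectable change at 80% power, in SDs of the difference (noncentral t), is:

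| Pairs | At 0.05 | At 0.05/3 |
|---|---|---|
| 120 (best case) | 0.26 | 0.30 |
| 80 (assumed) | 0.32 | 0.37 |
| 40 (assumed) | 0.45 | 0.53 |

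The smallest row is relevant because section 3.4 requires a participant to "Be a practitioner of one of the modalities investigated for more than 5 years" and does not say whether non-swimmers take the swimming test. An effect with 80% power at 5% has about 65% at the strictest step. The normal approximation agrees: Φ(1.960 + 0.842 − 2.394) = Φ(0.408) ≈ 0.66. Holm's later steps lose less.

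**What Holm would leave untouched.** Suppose performance drifts by 0.2 SD over 90 days for reasons unrelated to dental care (assumed), with 120 pairs. One test then rejects 58% of the time at 5% and 41% at 0.05/3. With three independent tests all drifting, the chance of at least one rejection falls only from 1 − (1 − 0.584)³ = 93% to 1 − (1 − 0.409)³ = 79%.

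**The case for a change.** The best argument for a change is that it is cheap and narrow. It would need a sentence or two in section 3.6 and no new data. Holm requires no correlation and tolerates different numbers of athletes per test. It could be confined to the one claim that performance changed, leaving the dental comparisons alone. Secondary status does not prevent selective emphasis, and nothing in the plan rules out a headline built on the one favourable test. Above r = 0.5 the inflation shrinks but disappears only at perfect correlation.

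Much of this stands. The gap in the text is real, and the arithmetic is right on its assumptions. Three things limit its force. First, the inflated rate belongs to a claim the plan does not make. Second, a Holm step over three before-after ANOVA p-values would leave the GEE score tests involving the same measures at an unadjusted 5%, and section 3.6 also foresees both parametric and non-parametric analysis. The choice among p-values would thus stay open unless the whole set of analyses were rewritten. Third, naming a single main test instead would mean choosing among domains that the objective treats as equal, and the documents give no basis for that choice.

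**Conclusion.** No change to the plan follows. The missing adjustment is a fair trade-off for separate secondary domains in an uncontrolled before-after study of a convenience sample. The stated 5% is the correct error rate for each domain reported on its own, and no stated rule produces a wrong result.

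The size of the concern is conditional. If someone asserted a general change in performance on the strength of any one of three tests, the chance of a false assertion would be at most 14.3% with independent tests, 12.5% at r = 0.5 and 9.8% at r = 0.8. This assumes two-sided tests, one per domain, aerobic running standing for endurance, and no drift. Against that gain stands a fall in power from 80% to about 65% at Holm's strictest step. The larger threat to a performance claim, a change over 90 days unrelated to treatment, would remain almost as it was. Statisticians may reasonably differ on whether the gain is worth the cost. With p-values shown for all the tests, a reader can allow for their number.
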